4.3 Withdrawal

In accordance with the Declaration of Helsinki, each subject is free to withdraw from the study at any time and without providing a reason.

A subject who withdraws consent prior to administration of Tc 99m sulfur colloid at the study site on Day 0 will be considered a withdrawn subject.

Should a subject withdraw after administration of the investigational product, all efforts will be made to complete and report the observations up to the time of withdrawal as thoroughly as

Confidential Page 37 of 71

Clinical Study Protocol Number: NAV3-30

possible. An explanation should be given of why the subject is withdrawing or being withdrawn from the study.

The investigator may withdraw a subject from the study at any time at the discretion of the investigator for any of the following reasons:

- A protocol violation occurs
- A serious or intolerable AE occurs
- A clinically significant change in a laboratory parameter occurs
- At the investigator's/sponsor's discretion as long as it is in the best interest of the subject
- The sponsor or investigator terminates the study
- The subject requests to be discontinued from the study

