7.2.3.3 After Administration of Tc 99m Tilmanocept

The following procedures will be completed at the specified times:

- 20 ± 5 Minutes After Administration:
 - Assessment of AEs
 - o ECG (completed before vital signs)
 - Vital signs after at least 1 minute in a resting position (body temperature, heart rate, blood pressure, and respiratory rate)
 - o Planar imaging of the liver/spleen followed by SPECT/CT of the liver/spleen and abdomen
- 75 ± 15 Minutes After Administration:
 - Assessment of AEs

Confidential

Clinical Study Protocol Number: NAV3-30

- o Planar imaging of the liver/spleen followed by SPECT/CT of the liver/spleen and abdomen
- 180 ± 15 Minutes After Administration:
 - Assessment of AEs
 - o Planar imaging of the liver/spleen followed by SPECT/CT of the liver/spleen and abdomen
- After Completion of All Imaging:
 - o Blood draw for hematology and chemistry testing
 - o Urine collection for urinalysis

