8.4 Safety

8.4.1 Adverse Events

8.4.1.1 Definition of Adverse Event

The definitions below follow International Conference on Harmonization (ICH) – Good Clinical Practice (GCP) (see also ICH Guideline for Clinical Safety Data Management: Definitions and Standards for Expedited Reporting).

Adverse Event (AE)

An AE is defined as any untoward medical occurrence in a subject administered a pharmaceutical product and which does not necessarily have a causal relationship with this treatment. An AE can therefore be any unfavorable and unintended sign (including an abnormal laboratory finding), symptom, or disease temporally associated with the use of a medicinal (investigational) product, whether or not considered related to the medicinal (investigational) product.

Any clinically significant change in a condition (worsening) from screening that results in a change in subject management will be considered an AE and will be recorded on the AE page of the CRF.

By definition for this study, all untoward medical occurrences beginning on the day of Visit 1 Screening (Days -45 to -1) through the assessment of the Safety Follow-up Telephone Call (Day 8 ± 3) are to be reported as AEs. AEs continuing after study completion will be followed to normalization or stabilization. SAEs will be reported from the time of consent through the end of participation.

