8.4.2.4 Clinical Laboratory Parameters for Screening and Safety

Clinical laboratory tests to be evaluated in this study include hematology, serum chemistry, and urinalysis. Clinical laboratory tests will include the following as defined in Table 2.

Table 2. Clinical Laboratory Parameters

Hematology	Hemoglobin (Hgb), hematocrit (HCT), platelets, neutrophils, basophils, lymphocytes, monocytes, red blood cells (RBC), white blood cells (WBC)
Serum chemistry	Aspartate aminotransferase (AST), alanine aminotransferase (ALT), alkaline phosphatase, total bilirubin, creatinine, chloride, hemoglobin A1c (screening only), potassium, sodium, total protein, albumin, carbon dioxide (CO ₂)/bicarbonate, blood urea nitrogen (BUN), glucose
Urinalysis	pH, specific gravity

All laboratory reports must be promptly reviewed for clinical significance by the investigator, and upon review, initialed and dated by the investigator.

Good clinical practice would suggest that a copy of the laboratory results also be provided to the subject's referring physician.

Any change in a laboratory value, which results in a change in subject management (additional controls or treatment required), will be reported as a clinically significant change. Clinically significant changes in laboratory parameters, which are not the result of laboratory error, are to be recorded as AEs.

Clinical Study Protocol Number: NAV3-30

Any clinically significant changes in laboratory values are to be followed up with repeated tests at appropriate intervals (as determined by the investigator) until the values return to baseline level or until the abnormality is explained by the investigator.

The expected amount of blood to be withdrawn is shown in Table 3.

Table 3 Approximate Amount of Blood Withdrawn

Time point of examination		Blood Volume
Screening: Laboratory examination	Chemistry 5 mLs Hematology 4 mLs	9 mL (~2 tsp)
Post Tilmanocept Injection and Imaging: Laboratory examination	Chemistry 5 mLs Hematology 4 mLs	9 mL (~2 tsp)
TOTAL:		18 mL (~4 tsp)

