9.2 Safety Variables

The primary variable for this study is whether a subject observes any noxious pharmacologic activity/adverse drug reaction (ADR) during their enrollment in the trial. This is a safety endpoint. The pharmacologic activity or ADR must be observed after the dose of Tc99m tilmanocept is administered.

NOTE: Adverse Drug Reaction

An ADR includes all noxious and unintended responses to a medicinal product related to any dose or dose regimen. The phrase "responses to a medicinal product" means that a casual relationship between a medicinal product and an AE is at least a reasonable possibility, i.e. the relationship cannot be ruled out.

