Appendix 1 Schedule of Events

	Visit 1 Screening	Visit 2 Day 0 Tc 99m sulfur colloid Administration				
Evaluation	Days -45 to -1	Day 0 Prior to Administration	- 00:15 to -00:01 Mins	00:00	20 ± 5 Mins	
Informed Consent	x					
Entry Criteria	х					
Medical History, Demography	х					
Vital Sign Assessment	х		X		X	
ECG	х					
Physical Examination	х					
Clinical Laboratory Evaluation: Chemistry, Hematology and UA	х					
Hemoglobin A1c Evaluation	x					
Pregnancy Test	x ^a	x ^a				
Transient Elastography	X					
Sulfur Colloid Administration				X		
Tilmanocept Administration						
Planar and SPECT/CT Liver Imaging					X	
Concomitant Medications	X	х	_			
Adverse Event Monitoring	x	X	X	Х	X	

a. Pregnancy test at screening will be serum; Day 0 and Day 3 pregnancy tests will be urine.

Confidential Page 68 of 71

b. Collection of samples for laboratory evaluation will occur after completion of all imaging procedures.

	Visit 3 Day 3 Tc 99m tilmanocept Administration					Follow-up Telephone Call	
Evaluation	Day 3 Prior to Administration	- 00:15 to -00:01 Mins	00:00	$20 \pm 5 \text{ Mins}$	75 ± 15 Mins	180 ± 15 Mins	Day 8 ± 3
Informed Consent							
Entry Criteria							
Medical History, Demography							
Vital Sign Assessment		х		X			
ECG				X			
Physical Examination							
Clinical Laboratory Evaluation: Chemistry, Hematology and UA						x ^b	
Pregnancy Test	X ^a						
Transient Elastography							
Sulfur Colloid Administration							
Tilmanocept Administration			X				
Planar and SPECT/CT Liver Imaging				х	X	х	
Concomitant Medications	X						X
Adverse Event Monitoring	X	Х	X	x	X	х	X

a. Pregnancy test at screening will be serum; Day 0 and Day 3 pregnancy tests will be urine.

Confidential Page 69 of 71

b. Collection of samples for laboratory evaluation will occur after completion of all imaging procedures.

Clinical Study Protocol Number: NAV3-30

Navidea Biopharmaceuticals, Inc

Date: 26-April DUT 8

Date: 23 April 2018

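### A subject who leaves after tilmanocept need not have the Day 8 ± 3 safety follow-up, yet stays in the Safety Population and can count as having no ADR on shortened observation

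*Combined protocol and SAP*

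**What the plan says.** Section 4.3 covers subjects who withdraw after receiving the product: "all efforts will be made to complete and report the observations up to the time of withdrawal", with an explanation of the reason. It then lists grounds on which the investigator may withdraw a subject. These include "A serious or intolerable AE occurs" and "A clinically significant change in a laboratory parameter occurs", and also a protocol violation.

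The end of safety observation is described in several ways:

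- Section 8.4.1.1 reports adverse events from screening to the safety call at Day 8 ± 3.
- The same section ends serious event reporting differently: "SAEs will be reported from the time of consent through the end of participation".
- Section 9.2 defines the primary variable as "whether a subject observes any noxious pharmacologic activity/adverse drug reaction (ADR) during their enrollment in the trial", counted only after the tilmanocept dose.
- Section 9.5.4 observes adverse events until the subject exits the study.

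The only scheduled post-dose blood and urine samples come under the entry "After Completion of All Imaging" in Section 7.2.3.3. Footnote b of Appendix 1 repeats this: "Collection of samples for laboratory evaluation will occur after completion of all imaging procedures". The schedule has no early-termination assessment.

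The Safety Population (Section 9.5.1) needs both administrations and sets no minimum follow-up. Section 4.4 replaces subjects who did not receive both products or did not go on to imaging. The missing-data rule in Section 9.5.5 names efficacy variables only.

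**The concern.** The primary endpoint is the proportion of subjects with an ADR after tilmanocept, so a subject recorded as having none should have been observed for the planned period. Each product is a single injection. After the tilmanocept injection, leaving the study spares the remaining scans but no further dose, and it ends scheduled safety observation.

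For such a subject the plan gives two possible ends to the window: the call date, or the day of exit. The default reading is the shorter one, and nothing in the protocol says how the subject is counted or shown. The post-dose laboratory sample is exposed in a similar way, since its timing is defined only relative to finished imaging. Data not collected in these days cannot be recovered at analysis, whatever a statistical analysis plan later specifies.

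**Working it through.** **Length of follow-up at risk.** The call is planned 5 ± 3 days after tilmanocept (Sections 3.1 and 7.2.4): 5 − 3 = 2 days to 5 + 3 = 8 days. With tilmanocept on Day 3, that is Day 5 to Day 11. Section 3.4 gives up to 57 days on study, which is reproduced by ending at the latest call: 45 screening days + Day 0 + 11 days = 57. So the call is the planned end of participation, and an exit on Day 3 can lose nearly all of the 2 to 8 days.

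**Who is affected.** By point of exit:

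| Exit | In Safety Population? | Replaced? | Effect on the ADR proportion |
|---|---|---|---|
| Between sulfur colloid and tilmanocept | No | Yes | None |
| After tilmanocept and a first scan, event already judged related | Yes | No | None: already in the yes/no numerator |
| After tilmanocept and a first scan, no related event so far | Yes | No | A later first ADR may go unrecorded |

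Only the last row is a gap. Section 8.4.1.2 counts possibly related events as related, which makes the second row wider and the third narrower.

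**Events already present at exit.** Section 8.4.1.1 follows continuing adverse events beyond study completion until they normalize or stabilize. For laboratory values, Section 8.4.2.4 says "Any clinically significant changes in laboratory values are to be followed up with repeated tests". Neither exempts withdrawn subjects. What remains uncovered is new-onset events, and samples never drawn.

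**Imaging before the laboratory sample.** Section 8.2 anticipates 25–30 minutes for each planar or SPECT/CT scan. Three sessions × 2 scans × 25–30 minutes = 150–180 minutes, with breaks. If a subject stops part-way, neither Section 7.2.3.3 nor footnote b says when, or whether, the sample is taken.

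**Planned number.** Section 9.4 gives N = 12 with no rate, precision or power. The longest route in Section 5.2 reproduces it: 2 + 1 + 3 + 3 + 3 = 12. The trial could also end at 2 + 1 + 3 = 6, or at 2 + 3 + 3 = 8 if the first review selects the lower radiolabel dose.

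**Effect of one subject of unknown status.** The shift is 1/n:

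- 12 subjects: 1/12 = 8.3 points
- 6 subjects (one subject type at full enrolment): 1/6 = 16.7 points
- 3 subjects (one subject type at one dose level): 1/3 = 33.3 points

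Illustration with exact (Clopper-Pearson) 95% intervals, assuming one such subject and no ADR in anyone else:

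| Handling | Proportion | 95% interval |
|---|---|---|
| Kept, counted as no ADR | 0/12 = 0% | 0% to 26.5% |
| Excluded | 0/11 = 0% | 0% to 28.5% |
| Counted as an ADR | 1/12 = 8.3% | 0.2% to 38.5% |
| Group of 6, counted as no ADR | 0/6 = 0% | 0% to 45.9% |
| Group of 6, counted as an ADR | 1/6 = 16.7% | 0.4% to 64.1% |

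The first review of tilmanocept safety rests on two subjects (Section 5.2), so one with shortened follow-up would be half of its evidence.

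**The case against.** Several stronger readings are tempting, and the documents do not support them.

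- **That withdrawal for an adverse event or laboratory change hides ADRs and biases the proportion downward.** The endpoint is yes/no per subject. If the event that led to withdrawal came after tilmanocept and was judged related, the subject is already counted, and shorter follow-up cannot undo that. These grounds are where truncation matters least.
- **That Section 4.3 forbids later collection or contradicts Section 8.4.2.4.** It sets a minimum. Existing events and laboratory changes are carried forward elsewhere. The sections are unreconciled for new events; they do not contradict each other.
- **That the sample is omitted when imaging stops early.** The wording gives a sequence and is silent on this case.
- **That a proportion would fall from 33%, 20% or 17% to 0%** (one ADR in 3, 5 or 6 NASH subjects). This requires the group's only ADR to begin after exit and never be reported. It is a worst case.

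Other points for the plan carry weight. The data sentence in Section 4.3 opens with subjects who withdraw themselves, for whom the wording is ordinary; its reach to investigator withdrawal is inferred from the next sentence. Section 8.4.1.5 requires notice within 24 hours of any serious event over the course of the study, though it does not say that this continues for someone whose participation has ended. Section 9.5.4 leaves further safety analyses to a statistical analysis plan whose text is not in the supplied document, so it cannot be said that the analysis ignores the problem. The study is descriptive, has at most 12 evaluable subjects, and follows them for at most 8 days after tilmanocept.

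These points narrow the gap but do not close it. No section requires the call for a dosed subject who leaves, or fixes one end to the ADR window for that subject.

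**Conclusion.** The point holds in a limited form. A subject who leaves after tilmanocept and a first scan, with no related event so far, remains in the denominator and can count as having no ADR on follow-up that may miss the 2 to 8 days up to the call. The post-dose blood and urine are also unsecured if imaging stops early.

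The possible effect is at most 8.3 points per subject of unknown status in 12, 16.7 in 6 and 33.3 in 3. These are bounds. The documents give no withdrawal rate or ADR rate, so neither an expected bias nor its probability can be calculated. The conclusion assumes that the sections are read as written and that no analysis plan outside the supplied text adds a collection rule. It is a worthwhile low-cost improvement to the primary endpoint, not a flaw that invalidates the study.

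**What to change.** 1. In Section 4.3, separate stopping study procedures from refusing further contact. For any subject who has received tilmanocept and has not refused contact, still collect the outstanding scheduled safety assessments: the 20-minute ECG and vital signs if not yet done, the post-dose blood and urine, and the Day 8 ± 3 call. Run adverse event and serious event reporting to the date on which the call would have fallen.
2. Align Sections 8.4.1.1, 9.2 and 9.5.4 to that single end of the window.
3. In Section 7.2.3.3 and footnote b of Appendix 1, time the sample after the last imaging performed, or when imaging is stopped.
4. In the ADR table, show how many subjects completed the Day 8 ± 3 follow-up.

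The cost is protocol wording and some site effort to reach subjects who have left. No new procedure is added, since every item is already scheduled for all subjects, and a refusal of contact is respected.

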4.4 Replacement

Subjects will be replaced under the following conditions:

Subjects who did not receive both unfiltered Tc 99m sulfur colloid and Tc 99m tilmanocept administration or did not proceed to imaging following either administration.

4.5 Subject Identification

After the subject provides written informed consent, the site will assign the subject a 7-digit subject number. Subject numbers are to be assigned in a sequential manner using the following format:

```
Digits 1 to 2: Study number "30"
```

Digits 3 to 4: Site number (e.g., "01")

Digits 5 to 7: Sequential subject number (e.g., "001", "002", "003")

For example, the first subject consented at Site 01 is subject number "30-01-001."

Subjects will maintain the same number given at screening for the entire study. If a subject is a screen failure, the number will not be used for any other subject.

5 INVESTIGATIONAL PRODUCT

5.1 Identification of Investigational Product

Tc 99m tilmanocept is a radiopharmaceutical that binds to mannose binding receptors (CD206) that reside on the surfaces of dendritic cells and macrophages.

5.2 Investigational Product Dosage and Administration

[figure not shown]
On Day 0, subjects will receive an on label 8.0 mCi dose of unfiltered Tc 99m sulfur colloid via IV administration. On Day 3, subjects will receive 200 μg tilmanocept via IV administration at the specified radiolabeled dose of Tc 99m. A single syringe will be used for each product and injected as a slow push into the IV. At the completion of each injection, a 10 cc sterile normal saline flush will be administered. The preferred site of IV placement will be the left or right antecubital vein. The final administered tilmanocept dose will be \pm 20% of the mass dose and radiolabel mCi dose assignment.

The first two enrolled subjects will be NASH subjects who will receive an 8.0 mCi radiolabel dose of Tc 99m tilmanocept. A review meeting will be held following completion of the first two subjects to evaluate tilmanocept safety and dose performance.

At the review (as diagrammed below):

- 1. If it is determined that a lower radiolabel dose of tilmanocept may produce images of better quality, three additional NASH subjects and three HCs will be injected and imaged with 200 µg of 2.5 mCi Tc 99m tilmanocept. After these six subjects have completed the trial, no additional subjects will be enrolled.
- 2. If the review shows no safety signals and acceptable quality of imaging, one additional NASH subject as well as three HCs will be injected and imaged with 200 μg of 8.0 mCi Tc 99m tilmanocept. Once a total of three NASH subjects and three HCs have completed the trial, a second review meeting will be held to compare results from NASH subjects to those of the HCs. If it is determined at the second review meeting that a lower radiolabel dose of tilmanocept may produce additional clinically meaningful results, 3 NASH subjects and 3 HCs will be dosed with 200 μg of 2.5 mCi Tc 99m tilmanocept. If it is determined that additional doses will not provide clinically meaningful results, the trial will be concluded.

Confidential Page 39 of 71

5.3 Treatment Assignment

In this prospective, open-label, non-randomized, multicenter, safety, comparative study, all subjects will receive IV administration of both 8.0 mCi unfiltered Tc 99m sulfur colloid and 200 µg tilmanocept at the specified radiolabeled Tc 99m dose. After the completion of two

NASH subjects at the 8.0 mCi radiolabel dose of Tc 99m tilmanocept, the tilmanocept dose

5.4 Packaging and Labeling

will reviewed, as detailed in Section 5.2.

Unfiltered Tc 99m sulfur colloid will be prepared at an on label 8.0 mCi dose according to standard clinical practice by Nuclear Medicine technologists at the clinical site [36].

The dose of Tc 99m tilmanocept should be ordered from Cardinal Health once the subject has been scheduled for IV administration and imaging.

Tilmanocept cartons ready for radiolabeling will be shipped and stored at the region-specific Cardinal Health radiopharmacy. Tilmanocept is provided in a vial. Vials are packaged as a kit. A carton contains five vials of tilmanocept. One kit, which contains one tilmanocept vial, should be used for no more than one subject. The carton also contains five shield labels and 25 syringe labels. This package has been designed specifically for tilmanocept and protects the vials during shipment, handling, and storage. Navidea will provide a radiolabeling protocol and Quality Control worksheets. The Cardinal Health radiopharmacy will radiolabel the specified tilmanocept dose at the assigned millicurie dose Tc 99m in 1.0 mL and deliver one syringe to the clinical site radiopharmacy that is ready for administration.

5.5 Drug Logistics and Investigational Product Accountability

The investigator (or designated personnel) will confirm receipt of the investigational product in writing and will use the investigational product only within the framework of this clinical study and in accordance with this study protocol. For each subject, he/she will keep a record of the investigational product dispensed and store all other forms that accompanied the delivery of the radiolabeled product to the clinical site. These documents are to be filed in the investigator site file. Overall drug accountability and reconciliation will be completed by the sponsor or its representative. A list of investigational product vials and other materials that were returned or destroyed must be recorded and signed by the PI or an appropriately qualified designee as documented in the study site responsibility sheet. An overall accountability and reconciliation form of the investigational product will be prepared and completed. If there are any discrepancies, they must be investigated and their resolution documented. All unused study kits will be destroyed in accordance with institutional destruction procedures.

Confidential Page 41 of 71

6 THERAPIES OTHER THAN INVESTIGATIONAL PRODUCT

6.1 Prior and Concomitant Therapy

All medications taken 30 days prior to the first screening visit through the 5 ± 3 days post-tilmanocept injection (Day 8 ± 3) safety follow-up telephone call will be documented. Subjects receiving radiation therapy or chemotherapy within 12 months of tilmanocept injection or who have been diagnosed with cancer other than basal cell carcinoma are not eligible for participation in the trial. The subject's history of treatments for NASH will also be collected.

